8.10.6. Visit 6 (Follow-up: 28 to 42 to Days After Dose 4)

NOTE: For the United States and Puerto Rico country-specific amendment related to Visit 6, please refer to Section 10.9.

- Ensure and document that the participant continues to be eligible for the study (see Section 7.2 for participant withdrawal information).
- Confirm whether the parent(s)/legal guardian(s) still possesses the participant contact card.
- Review the participant's e-diary data with the participant's parent(s)/legal guardian(s); collect stop dates of any e-diary events ongoing on the last day that the e-diary was completed and record stop dates in the CRF.
- Collect the e-diary (if applicable).
- Determine whether any AEs (includes nonserious AEs, SAEs, and NDCMCs) have occurred since the previous visit and follow up on any previously reported events to determine the outcome (ie, record stop dates or confirm if they are still continuing) and record as described in Section 10.3, and record concomitant medications used to treat NDCMCs and SAEs.
- Remind the participant's parent(s)/legal guardian(s) to contact the investigator or investigator site staff immediately if any significant illness or medical event (eg, emergency room visit or hospitalization) occurs.
- The investigator or an authorized designee completes the CRF.

8.10.7. Visit 7 (Follow-up: 168 to 196 Days After Dose 4)

NOTE: For the United States and Puerto Rico country-specific amendment related to Visit 7, please refer to Section 10.9.

- Contact the participant's parent(s)/legal guardian(s) by telephone approximately 6 months after the last study vaccination; this contact should be attempted for all participants who have received at least 1 study vaccination, unless the participant's parent(s)/legal guardian(s) has withdrawn consent.
- Determine whether any SAEs and NDCMCs have occurred since the previous visit and follow up on any previously reported events to determine the outcome (ie, record stop dates or confirm if they are still continuing) and record as described in Section 10.3, and record concomitant medications used to treat SAEs and NDCMCs.
- The investigator or an authorized designee completes the CRF and the source documents.

8.10.8. Unscheduled Visits

If the participant's parent(s)/legal guardian(s) reports redness or swelling at the injection site measuring >14 measuring device units (>7 cm) or severe injection site pain or a fever >40.0°C (>104.0°F) during the 7-day postvaccination period, a telephone contact must occur as soon as possible between the investigator or medically qualified designee and participant's parent(s)/legal guardian(s) to assess if an unscheduled investigator site visit is required. Note that for a fever >40.0°C (>104.0°F), the participant's parent(s)/legal guardian(s) should be instructed not to delay seeking medical care, as appropriate, while arranging for an unscheduled visit, if needed. A visit should be scheduled as soon as possible to assess the extent of the injection site reaction, unless any of the following is true:

- The participant's parent(s)/legal guardian(s) is unable to bring the participant to the unscheduled visit.
- The reaction is no longer present at the time of the telephone contact.
- The participant's parent(s)/legal guardian(s) recorded an incorrect value in the e-diary (confirmation of an e-diary data entry error).
- The principal investigator (PI) or authorized designee determined it was not needed.

This telephone contact will be recorded in the participant's source documentation and the CRF.

If the participant's parent(s)/legal guardian(s) is unable to bring the participant to an unscheduled visit, or the PI or authorized designee determined it was not needed, any ongoing reactions must be assessed at the next study visit.

During the investigator site visit, the reactions should be assessed by the investigator or a medically qualified member of the study staff such as a study physician or a study nurse, as applicable to the investigator's local practice, who will:

- Measure temperature (as appropriate for the age of the child, according to routine local practice [°F/°C]).
- Measure minimum and maximum diameters of redness (if present).
- Measure minimum and maximum diameters of swelling (if present).
- Assess injection site pain in accordance with the grades provided in Section 8.2.2 (if present).
- Assess for other findings associated with the reaction and record on the AE page of the CRF, if appropriate.

The investigator or an authorized designee will complete the unscheduled visit assessment page of the CRF.

The participant's parent(s)/legal guardian(s) will also be instructed to contact investigator site staff if the participant experiences any emergency room visit or hospitalization for decreased appetite, drowsiness/increased sleep, irritability, or local reaction within 7 days of vaccination.

The participant's parent(s)/legal guardian(s) will also be instructed to contact the investigator site to report any significant illness, medical event, or hospitalization that occurs during the study period. The investigator site should determine if an unscheduled visit to further evaluate the event is warranted in all such cases.

Additionally, study staff may contact the participant's parent(s)/legal guardian(s) to obtain additional information on Grade 3 events entered into the e-diary.

9. STATISTICAL CONSIDERATIONS

Detailed methodology for summary and statistical analyses of the data collected in this study is outlined here and further detailed in a statistical analysis plan (SAP), which will be maintained by the sponsor. The SAP may modify what is outlined in the protocol where appropriate; however, any major modifications of the primary endpoint definitions or their analyses will also be reflected in a protocol amendment.

9.1. Estimands and Statistical Hypotheses

9.1.1. Estimands

The primary objective of the study is to describe the safety profile of 20vPnC in healthy infants. Estimands to address the primary objective are provided in Section 3. In the safety evaluation, missing e-diary data will not be imputed. Missing AE dates will be imputed according to Pfizer safety rules. No other missing information will be imputed in the safety analysis.

There is no formal hypothesis test for any safety results.

9.2. Sample Size Determination

The study size in each vaccine group is not based on any formal hypothesis test for any safety endpoints. All statistical analyses will be descriptive.

The primary safety objectives include the endpoints for AEs reported between Dose 1 and 1 month after Dose 3 and also between Dose 4 and 1 month after Dose 4. The number of participants receiving 20vPnC is 1000, which provides a greater than 95% chance of observing at least 1 AE in this group, assuming a true rate of at least 0.3% (Table 4).

 Table 4.
 Probability of Detecting at Least 1 AE in the 20vPnC and 13vPnC Groups

Group	Sample Size	True Rate of AEs	Probability of Observing at Least 1 AE
20vPnC	1000	0.1%	63.2%
		0.2%	86.5%
		0.3%	95.0%
		0.4%	98.2%
		0.5%	99.3%
13vPnC	500	0.1%	39.4%
		0.2%	63.2%
		0.3%	77.7%
		0.4%	86.5%
		0.5%	91.8%

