2.1. Study Rationale

CCI

The purpose of the study is to assess the safety of 20vPnC in infants, and to provide key safety data to support licensure in this population. The targeted age of the population for this study, infants \geq 42 to \leq 98 days of age, has been selected as this is the routinely recommended age for initial vaccination with pneumococcal conjugate vaccines and other vaccines in infants. The participants will be administered either 20vPnC or 13vPnC at 2, 4, 6, and 12 to 15 months of age.

Amendment 1 is a United States and Puerto Rico country-specific amendment, which is being implemented to complete the vaccination schedule in a timely manner, as all participants are age-eligible for their final dose (Dose 4) as of the amendment date. There is no benefit to the participant to delay completion of the series. Delaying vaccination and in-person study visits in the trial also carries a risk of even further delays in vaccination and exposure risks that may occur with a potential resurgence of coronavirus disease in the near future. Finally, the 20vPnC pediatric program has been granted Breakthrough Therapy designation by the Food and Drug Administration (FDA), indicating that it has the potential to meet an unmet medical need to prevent serious disease in the pediatric population. Therefore, avoiding further delays in study completion will support our shared goal of generating the key data with 20vPnC in this vulnerable population and, if successful, allow this vaccine to be licensed and available to help protect young children as soon as possible. The modifications in this amendment impact only a very small overall proportion of participants who have not yet received Dose 4 and those who received Dose 4 after a certain date, and do not adversely affect the safety, scientific integrity, or management of the study.

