4.1.2. Approximate Number of Participants

Approximately 1500 participants will be randomized (approximately 1000 in the 20vPnC group and approximately 500 in the 13vPnC group).

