8.10.5. Visit 5 (Dose 4: 365 to 455 Days of Age)

NOTE: For the United States and Puerto Rico country-specific amendment related to Visit 5, please refer to Section 10.9.

- Ensure and document that the participant continues to be eligible for the study (see Section 7.2 for participant withdrawal information) and none of the temporary delay criteria are met (Section 5.5).
- Confirm whether the parent(s)/legal guardian(s) still possesses the participant contact card.
- Determine whether any SAEs and NDCMCs have occurred since the previous visit and follow up on any previously reported events to determine the outcome (ie, record stop dates or confirm if they are still continuing) and record as described in Section 10.3, and record concomitant medications used to treat NDCMCs and SAEs. Measure and record the participant's prevaccination temperature using a method appropriate for the age of the child, according to routine local practice (°F/°C).
- Administer a single 0.5-mL injection of investigational product (20vPnC or 13vPnC) into the anterolateral left thigh.
- If applicable, administer routine pediatric vaccinations into a limb other than the site of 20vPnC or 13vPnC injection and capture all details of the concomitant vaccine given on the same day as investigational product administration, including the name, date of administration, and site of administration, on the CRF.

After vaccination:

- Site staff will observe the participant for 30 minutes after vaccination for any reactions. Record any AEs on the CRF and on an SAE form as applicable. Record concomitant medications used to treat SAEs and NDCMCs.
- Issue the participant's parent(s)/legal guardian(s) an e-diary (device or application). Review and provide instructions on use and completion of the e-diary. Ask the participant's parent(s)/legal guardian(s) to complete the e-diary from Day 1 to Day 7, with Day 1 being the day of investigational product vaccination. Provide the participant's parent(s)/legal guardian(s) with a thermometer or measuring device if needed.

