- The CRF will be completed as thoroughly as possible and signed by the investigator before transmittal to the sponsor or designee.
- It is very important that the investigator provides his/her assessment of causality (relationship to the medical device provided by the sponsor) at the time of the initial AE or SAE report and describes any corrective or remedial actions taken to prevent recurrence of the incident.
- A remedial action is any action other than routine maintenance or servicing of a medical device where such action is necessary to prevent recurrence of an incident. This includes any amendment to the device design to prevent recurrence.

10.9. Appendix 9: Amendment 1 Country-Specific Requirements – Applicable to United States and Puerto Rico Only

Per Protocol Amendment 1, the following list summarizes the modifications of the protocol that are specific to sites in the United States and Puerto Rico only. The modifications impact Visit 5 and Visit 7 timing, and add flexibility in the format of Visit 6 as follows:

- Per Protocol Amendment 1: The last day to be eligible for Dose 4 (Visit 5) is 20 Apr 2022. Participants who have not received Dose 4 by this date are ineligible and will be discontinued per Section 7 of the protocol.
- Per Protocol Amendment 1: Visit 6 may be conducted by telephone.
- Per Protocol Amendment 1: The window for Visit 7 is modified for participants who have Visit 5 (receive Dose 4) after 16 Feb 2022:
 - Visit 5 performed on 17 Feb 2022 through 14 Mar 2022: the target Visit 7 window remains 168 to 196 days after Visit 5, but Visit 7 is to be completed by 31 Aug 2022, whichever is earlier.
 - Visit 5 performed on 15 Mar 2022 through 01 Apr 2022: the window is 145 to 168 days after Visit 5, or until 31Aug 2022, whichever is earlier.
 - Visit 5 performed on 02 Apr 2022 through 20 Apr 2022: the window is 126 to 145 days after Visit 5, or until 31Aug 2022, whichever is earlier.

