## 4. ANALYSIS SETS (POPULATIONS FOR ANALYSIS)

Analysis populations are defined for the statistical analysis of safety results in the table below. Data for all participants will be assessed to determine if participants meet the criteria for inclusion in each analysis population prior to unblinding and releasing the database for analysis, and the classifications will be documented per standard operating procedures.

Population	Description
Enrolled	All participants who sign the ICD.
Randomized	All participants who are assigned a randomization number in the IRT system.
Safety	All participants who receive at least 1 dose of the investigational product with safety follow-up after any dose.
	Participants will be grouped according to the vaccine as administered in the safety analysis.
	Safety data after Dose 4 will be summarized for the subset of the safety population who also receive Dose 4 with safety follow-up after Dose 4.

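### Does the missing attrition allowance for the Dose 4 window undermine the 95% detection figure in Protocol Section 9.2?

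*Protocol*

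**What the plan says.** Protocol Section 9.2 states that the study size rests on no formal test and that all analyses are descriptive. It then introduces the adverse-event endpoints, the second window running to one month past the fourth dose: "The primary safety objectives include the endpoints for AEs reported between Dose 1 and 1 month after Dose 3 and also between Dose 4". The size argument comes next. It takes 1000 infants as the recipients of 20vPnC and says of this number: "which provides a greater than 95% chance of observing at least 1 AE in this group, assuming a true rate of at least 0.3"%. In Table 4 a sample-size column shows 1000 for 20vPnC and 500 for 13vPnC, beside the probability of at least one event at true rates from 0.1% to 0.5%.

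Protocol Section 4.1.2 describes the randomized numbers as "approximately 1000 in the 20vPnC group and approximately 500 in the 13vPnC group". SAP Section 4 sets the denominator for the later window, which also requires follow-up after that dose: "Safety data after Dose 4 will be summarized for the subset of the safety population who also receive Dose 4".

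Losses before Dose 4 are foreseen. Protocol Sections 7.1 to 7.3 cover discontinuation, withdrawal and loss to follow-up. Protocol Section 10.9 (Amendment 1, United States and Puerto Rico) sets 20 Apr 2022 as the last day for Dose 4 and adds: "Participants who have not received Dose 4 by this date are ineligible and will be discontinued per Section 7 of the protocol". On the reach of the amendment, which also covers some infants already given that dose, Protocol Section 2.1 says that its modifications "impact only a very small overall proportion of participants who have not yet received Dose 4". Neither document states an expected attrition rate or an expected number at Dose 4.

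**The concern.** One probability, computed at 1000, follows directly after a sentence naming two windows, so a reader will naturally apply it to both. The second window has a smaller denominator by definition and comes much later. Under the original visit windows, follow-up after Dose 4 ends 295 to 455 days after Visit 1, against 112 to 168 days for the first window. Amendment 1 replaced the age-based Visit 5 window for the remaining infants, so 455 days is not an upper limit for them.

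The figure also has almost no slack. At a 0.3% rate, 1000 infants give a probability only just above 95%, so the loss of a few infants takes it below. If the sentence is meant to cover the Dose 4 window, the only readable quantitative argument for the study size would be slightly too favourable for one of the two periods it introduces.

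**Working it through.** **Inputs.** n = 1000 (20vPnC) and 500 (13vPnC), with true rates r of 0.1% to 0.5%, from Protocol Section 9.2 and Table 4. The loss before the Dose 4 window is not given in the documents; 5%, 10% and 15% are assumptions for illustration.

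**Formula.** P(at least one event) = 1 − (1 − r)^n.

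**Step 1: reproduce Table 4.**

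| r | n = 1000 | Table 4 | n = 500 | Table 4 |
|---|---|---|---|---|
| 0.1% | 63.23% | 63.2% | 39.36% | 39.4% |
| 0.2% | 86.49% | 86.5% | 63.25% | 63.2% |
| 0.3% | 95.04% | 95.0% | 77.74% | 77.7% |
| 0.4% | 98.18% | 98.2% | 86.52% | 86.5% |
| 0.5% | 99.34% | 99.3% | 91.84% | 91.8% |

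All ten cells agree. The text's claim of more than 95% and the table's 95.0% are consistent, because the value is 95.044%.

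**Step 2: find the slack at 0.3%.** The smallest n for more than 95% is the first integer above ln(0.05)/ln(0.997) = 997.08, which is 998. At n = 998 the probability is 95.014%; at n = 997 it is 94.999%. The margin is tiny only because 95.04% lies next to a round number. The probability itself changes very slowly with n.

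**Step 3: apply assumed losses.** The rate detectable with 95% probability is 1 − 0.05^(1/n).

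| Assumed loss | 20vPnC n | P at 0.3% | Rate detectable at 95% | P at 0.4% | 13vPnC n | P at 0.3% |
|---|---|---|---|---|---|---|
| 0% | 1000 | 95.0% | 0.299% | 98.2% | 500 | 77.7% |
| 5% | 950 | 94.2% | 0.315% | 97.8% | 475 | 76.0% |
| 10% | 900 | 93.3% | 0.332% | 97.3% | 450 | 74.1% |
| 15% | 850 | 92.2% | 0.352% | 96.7% | 425 | 72.1% |

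At 5% and 10% loss the detectable rate still rounds to the 0.3% in the text.

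**Step 4: check the next printed rate.** At 0.4%, ln(0.05)/ln(0.996) = 747.43, so more than 95% holds down to 748 infants, or with up to 252 of 1000 lost. That row is already in Table 4.

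**Step 5: check the time spans (original windows).** End of the Dose 4 window after Visit 1: (365 − 98) + 28 = 295 days to (455 − 42) + 42 = 455 days. First window: 42 + 42 + 28 = 112 days to 63 + 63 + 42 = 168 days.

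**Step 6: check what will be reported.** SAP Sections 5.2.1 and 6.1.1.3.1 give n, N, percentage and Clopper-Pearson interval for adverse events in each window. SAP Section 6.4.2.1 tabulates how many infants received each dose and completed each follow-up visit. The precision achieved after Dose 4 will therefore be visible, whatever was assumed at planning.

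**The case for a change.** The strongest case for a change is that this sentence and its table carry the whole readable numerical argument for 1500 infants, so the figure should hold for each primary window it introduces. The plan foresees losses, the starting number is itself approximate, and three infants lost out of 1000 are enough to make the sentence untrue for Dose 4. One added sentence would settle it at no cost.

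Part of this stands. Table 4 makes no allowance for attrition before Dose 4. If the sentence is read as covering that window, the probability would probably fall a little short of 95%. A note that the table assumes no attrition, and that the 0.4% row is the safer one for Dose 4, would be accurate.

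The rest does not lead to a change. The sentence is conditional on 1000 recipients of 20vPnC and is true on that condition; it claims nothing about the Dose 4 subset. A threshold of 998 is more exact than a group described as approximately 1000 can support. The loss rates behind any shortfall are assumptions without a source in the documents. By Amendment 1 only a small number of infants had yet to receive Dose 4 (Protocol Section 4.1), so rewording the planning text then could not alter recruitment or conduct.

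**Conclusion.** No change follows. The printed figures are correct at the sample sizes printed beside them, and no number in the documents is shown to be wrong. What is missing is a qualifying remark about the Dose 4 denominator, which any analyst can supply from SAP Section 4 and the disposition table.

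The size of the issue is modest. If 5% to 15% of infants were lost before the Dose 4 window, the probability of seeing at least one event at a 0.3% rate would be 94.2% to 92.2% instead of 95.0%, and the rate detectable with 95% probability would be 0.315% to 0.352% instead of 0.299%. At 0.4% the probability stays above 95% with as few as 748 infants. These figures assume independent infants with a common event rate, and the loss rates are not from the documents. The study is descriptive, with no hypothesis, margin or stopping decision tied to this probability, so enrolment, analysis and conclusions would be the same with or without the remark.

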9.3. Populations for Analysis

For purposes of analysis, the following populations are defined:

Population	Description
Enrolled	All participants who have a signed ICD.
Randomized	All participants who are assigned a randomization number in the IWR system.
SafetyAll randomized participants who receive at least 1 dose of the investige product and have safety data after any dose.	

9.4. Statistical Analyses

The SAP will be developed and finalized before database lock for any of the planned analysis in Section 9.5.1 and will describe the participant populations to be included in the analyses and procedures for accounting for missing, unused, and spurious data. This section is a summary of the planned statistical analyses of the primary CCI endpoints, as applicable.

9.4.1. Safety Analyses

All safety analyses will be performed on the safety population.

Primary	• Descriptive statistics will be provided for each reactogenicity endpoint for each dose and vaccine group. Local reactions and systemic events from Day 1 through Day 7
	 after each dose will be presented by severity cumulatively across severity levels. Descriptive summary statistics will include counts and percentages of participants with the indicated endpoint and the associated Clopper-Pearson 95% confidence intervals (CIs). Between-group differences (20vPnC – 13vPnC) in percentage and 2-sided 95% CIs will be provided. The Miettinen and Nurminen method will be used to derive the 95% CI for the difference in percentages between vaccine groups. AEs will be categorized according to Medical Dictionary for Regulatory Activities (MedDRA) terms. A 3-tier approach will be used to summarize AEs. Under this approach AEs are classified into 1 of 3 tiers: (1) Tier 1 events are prespecified events o clinical importance and are identified in a list in the product's safety review plan; (2) Tier 2 events are those that are not Tier 1 but are considered "relatively common"; a MedDRA preferred term is defined as a Tier 2 event if there are at least 1% of participants in at least 1 vaccine group reporting the event; (3) Tier 3 events are those that are neither Tier 1 nor Tier 2 events. For both Tier 1 and Tier 2 events, the 95% CIs for the difference in percentage of participants reporting the events between the 20vPnC and 13vPnC groups will be calculated using the Miettinen and Nurminen method. In addition, for Tier 1 events, the asymptotic p-values will also be presented for the difference in percentage of participants reporting the events, based on the same test statistic and under the assumption that the test statistic is asymptotially normally distributed. There is no Tier 1 events for each vaccine group. SAEs will be categorized according to MedDRA terms. Counts, percentages, and the associated Clopper-Pearson 95% CIs of SAEs and NDCMCs from Dose 1 to 6 months after Dose 4 will be provided for each vaccine group.
Secondary	• There are no secondary endpoints in the study.

